2.3 Safety Objective

Evaluation of the incidence of adverse events.

3 OVERVIEW OF METHODOLOGY AND DESIGN

3.1 Overall Study Design

This study is a prospective, open-label, within-subject study of Lymphoseek in the detection of lymph nodes in subjects with known cancer of the cervix. The pathology status of non-SLNs in the pelvic lymphadenectomy will serve as the control. All subjects will receive a single dose of 50 µg Lymphoseek (2.0 mCi) prior to ILM. A sample size of 40 was selected in order to provide exploratory results for the primary and secondary objectives. The proposed study includes 3 visits: A screening visit for initial determination of eligibility and evaluation of clinical status (up to 30 days before injection), a baseline visit on the day of surgery, and a 24 ± 12 hour (telephone) safety follow-up.

The Schedule of Events (see [Appendix 1](#)) contains a list of all study procedures and time points. Study activities are described in detail in [Section 7](#).

3.2 Justification for Study Design and Population

This study is designed to evaluate the use of Lymphoseek as an ILM and SLNB agent in subjects with known cancer of the cervix by evaluating the FNR for identifying tumor-positive lymph nodes as determined by histopathological evaluation of sentinel and non-sentinel lymph nodes following pelvic lymphadenectomy. In addition, the concordance of detection rates of Lymphoseek and of dyes will be determined.

Pelvic lymphadenectomy, with or without ILM using a dye as the mapping agent, is the current standard of care for patients undergoing cervical tumor resection. Therefore, this study will directly evaluate Lymphoseek's performance relative to the standard of care.

3.2.1 Rationale for Subject Selection

No clinical trials have been conducted to evaluate Lymphoseek performance in subjects with cervical cancer. The rationale for evaluating Lymphoseek in this subject population is discussed in [Section 1.1.2](#).

[REDACTED]

[REDACTED]

[REDACTED]

3.3 Protocol Adherence

Strict adherence to all specifications laid down in this protocol is required for all aspects of the study conduct; the investigator may not modify or alter the procedures described in this protocol. If protocol modifications are necessary, all alterations that are not solely of an administrative nature require a formal protocol amendment (see [Section 11.1](#) for the involvement of International Ethics Committee(s) IEC(s)/ International Review Board(s) IRB(s)).

If an investigator has deviated from the protocol in order to eliminate an immediate hazard to subjects or for other inevitable medical reasons, the investigator shall document all such deviations, including the reasons thereof, and submit the document to the sponsor and the head of the medical institution as applicable.

Participating investigators must have 10 cases of intraoperative lymphatic mapping in gynecologic cancer patients to participate as a surgeon for any subjects enrolled in this trial.

3.4 Study Duration

Subjects will be enrolled for approximately 32 days depending on the duration of the screening window (up to 30 days).

4 STUDY POPULATION

4.1 Eligibility

Subjects who fulfill all respective inclusion and none of the exclusion criteria will be eligible for enrollment into the study. All inclusion/exclusion criteria must be verified before a subject may be considered eligible for injection and imaging (Day 1 procedures). A subject will be considered enrolled in the study on the morning of study day 1 when they arrive at the study site. Written, dated (with time noted) informed consent will be obtained from all subjects. A subject who withdraws consent prior to arrival at the study site on day 1 will be considered a screen failure.

4.1.1 Inclusion Criteria

1. Subject has provided written informed consent with HIPAA authorization
2. Has cervical cancer and is a candidate for surgical intervention, with lymph node dissection being a part of the surgical plan.
3. Is at least 18 years of age at the time of consent
4. Has an ECOG performance status of Grade 0 to 2
5. Has the following International Federation of Gynecology and Obstetrics (FIGO) IA2-IIA1(≤ 4 cm) staging(Appendix 5) Subjects with a single enlarged/suspicious node on PET CT will still be considered eligible as consistent with FIGO guidelines.
6. If of childbearing potential, the subject has a negative pregnancy test within 48 hours before administration of Lymphoseek, has been surgically sterilized, or has been postmenopausal for at least 1 year

4.1.2 Exclusion Criteria

1. The subject has had preoperative chemotherapy, immunotherapy, or radiation therapy within the 30 days prior to Lymphoseek administration
2. Has had previous surgery or radiation to node basins that would be involved in the ILM procedure
3. Has a known allergy to dextran
4. Is breast-feeding or pregnant
5. Before the administration of Lymphoseek, has received any radiopharmaceutical within 7 radioactive half-lives of that radiopharmaceutical
6. Is scheduled for surgery and/or another invasive procedure other than the primary surgical intervention within the 3 days after Lymphoseek administration
7. Has received an investigational product within the 30 days prior to Lymphoseek

administration

4.2 Recruitment

Subjects will be recruited from oncology practices in accordance with the inclusion and exclusion criteria listed above. Potentially suitable subjects will be asked by their treating physician about their willingness to participate in this study.

4.3 Withdrawal

In accordance with the Declaration of Helsinki, each subject is free to withdraw from the study at any time and without providing a reason.

A subject who withdraws consent prior to arrival at the study site on Day 1 will be considered a screen failure.

Should a subject withdraw after administration of the investigational product all efforts will be made to complete and report the observations up to the time of withdrawal as thoroughly as possible. An explanation should be given of why the subject is withdrawing or being withdrawn from the study.

The investigator may withdraw a subject from the study at any time at the discretion of the investigator for any of the following reasons:

- A protocol violation occurs
- A serious or intolerable AE occurs
- A clinically significant change in a laboratory parameter occurs
- At the investigator's/sponsor's discretion as long as it is in the best interest of the subject
- The sponsor or investigator terminates the study
- The subject requests to be discontinued from the study

4.4 Replacement

Subjects will be replaced under the following conditions:

- Subjects who did not receive study medication or did not proceed to surgery or did not undergo lymphatic mapping with lymph node biopsy.

4.5 Subject Identification

After the subject provides written informed consent, the site will assign the subject a 7-digit subject number. Subject numbers are to be assigned in a sequential manner using the following format:

Digits 1 to 2: Trial number “19”
Digits 3 to 4: Site number (e.g., “03”)

Digits 5 to 7: Sequential subject number (e.g., "001", "002", "003", etc.)

For example, the first subject consented at Site 03 is subject number "19-03-001".
Subjects will maintain the same number given at screening for the entire study. If a subject is a screen failure, the number will not be used for any other subject.

5 INVESTIGATIONAL PRODUCT

5.1 Identification of Investigational Product

Lymphoseek® (also known as technetium Tc 99m tilmanocept) is a radiopharmaceutical that accumulates in lymphatic tissue by binding to mannose binding receptors (CD206) that reside on the surfaces of dendritic cells and macrophages.

5.2 Investigational Product Dosage and Administration

Subjects will receive 50 µg tilmanocept radiolabeled with 2 mCi (74 MBq) Tc 99m administered as four separate injections. The total injection volume for each subject is 0.4 or 1.0 mL administered across all four syringes (0.1 or 0.25 mL each).

The dose will be prepared in 1 mL BD Luer-Lok syringes with a 0.5 inch needle. The needle should be replaced at the discretion of the investigator in accordance with site practices. A 22- to 24-gauge spinal or potocky needle is commonly used. In order to achieve accurate delivery of small volumes, final syringe volume adjustments will be made at the pharmacy to accommodate volume retained in the syringe hub and needle such that air should not be added to the syringe and no syringe flushing should occur.

Subjects will receive Lymphoseek by injection in a manner consistent with the European Association of Nuclear Medicine (EANM) clinical and technical guidelines for lymphoscintigraphy and sentinel node localization in gynaecological cancers as adopted by the Society of Nuclear Medicine and Molecular Imaging (SNMMI) ([Giamarile et al., 2014](#)). The agents for lymphatic mapping will be administered peritumorally as subepithelial (submucosal) instillations into the 4 quadrants of the cervix at the 12, 3, 6, and 9 o'clock positions whenever possible. Lymphoseek should not be injected directly into the tumor. For those subjects with little remaining normal cervical tissue, injections should be administered in the tissue surrounding the tumor with adjustment of the injection positions as necessary. Injection placement in relation to the cervix will be documented in the trial source. Subjects will be scheduled for surgery after imaging and no later than 20 hours after Lymphoseek injection and imaging. Just before surgical incision, a dye (e.g., VBD or ICG) may be injected in close proximity to the tumor. Preoperative evaluation of the subject will follow routine institution practice.

5.3 Dye Dosage and Administration

A dye, such as Lymphazurin (isosulfan blue 1%) or indocyanine green, may be administered to subjects as part of their standard of care. The injection will be performed as deemed appropriate by the surgeon and in accordance with the standard of care at the clinical site.

5.4 Treatment Assignment

In this open-label non-randomized study, all subjects will receive the same Lymphoseek treatment.

5.6 Drug Logistics and Accountability

The investigator (or designated personnel) will confirm receipt of the investigational product in writing and will use the investigational product only within the framework of this clinical study and in accordance with this study protocol. For each subject he/she will keep a record of the investigational product dispensed and store all other forms that accompanied the delivery of the radiolabeled investigational product to the clinical site. These documents are to be filed in the investigator site file. Overall drug accountability and reconciliation will be completed by the sponsor or its representative. A list of investigational product vials or syringes and other materials that were returned, or destroyed, must be prepared and signed by the principal investigator or an appropriately qualified designee as documented in the study site responsibility sheet. An overall accountability and reconciliation form of the investigational product will also be prepared and completed. If there are any discrepancies, an explanation for these must be provided.

6 THERAPIES OTHER THAN INVESTIGATIONAL PRODUCT

6.1 Prior and Concomitant Therapy

All medications taken 30 days prior to Lymphoseek injection through the 24-hour post-injection follow-up will be documented. Any subject that has had preoperative chemotherapy, immunotherapy, or radiation therapy within the 30 days prior to Lymphoseek administration will be excluded from the study.

6.2 Post-Study Therapy

There are no post-study therapy restrictions.

7 SCHEDULE OF EVALUATIONS AND VISIT DESCRIPTION

7.1 Schedule of Evaluations

Evaluations will be performed during a period of 2-3 days, in addition to a screening period of 30 days maximum. A schedule of evaluations is provided in the Schedule of Study Events (see [Appendix 1](#)).

7.2 Visit Description

7.2.1 Screening Visit (Day -29 to Day 0)

- Preliminary review of inclusion and exclusion criteria
- Obtain signed informed consent for study participation
- Allocation of unique subject number; this number will be used to document the subject data in the eCRF and enrollment log
- Demography – Date of birth, race and ethnicity
- Medical history – Medical history will be obtained on all study subjects. All relevant prior medical conditions will be recorded in the CRFs. Documented medical conditions will also note the month/year of onset and if the condition is active.
- Cancer staging – Tumor characteristics including FIGO staging information will be collected.
- ECOG performance status will be collected
- Vital signs – Vital signs will include respiratory rate, pulse rate, and systolic and diastolic blood pressures. Prior to obtaining blood pressures and pulse, the subject should be in a resting position for at least 1 minute. Body weight and height without shoes will be recorded only at the screening evaluation.
- Physical exam – Physical examinations will include examination of general appearance, skin, eyes, ears, nose, throat, head and neck (including thyroid), lungs, heart, abdomen, pelvis, lymph nodes, musculoskeletal, and nervous system. Physical exams that are conducted as standard of care prior to signing informed consent may be used if they are performed within 30 days of injection.
- Clinical laboratory tests - study subjects will have blood obtained for hematology and chemistry (See [Section 8.8.2](#)).
- Concomitant medications (within 30 days before injection).
- Final check of inclusion/exclusion criteria

7.2.2 Before Enrollment

Within 48 hours prior to receiving the Lymphoseek injection, a urine or serum pregnancy test will be conducted for female subjects of childbearing age.

All subjects will be questioned to determine if a change in medical history or concomitant medications has occurred since the last visit.

7.2.3 Preparation of Lymphoseek

The following medications are not permitted as co-injected drugs: local anesthetics, e.g., procaine, xylocaine, lidocaine, or carbocaine.

7.2.4 Before Injection

Before receiving the Lymphoseek injection vital signs will be collected. Vital signs will include respiratory rate, pulse rate, and systolic and diastolic blood pressures. A window of up to 10 minutes before injection is allowed. Prior to obtaining blood pressures and pulse, the subject should be in a resting position for at least 1 minute. Body weight and height measurements are not required.

7.2.5 Injection of Lymphoseek

Injection of Lymphoseek will be at study time 0:00. Subjects will receive 50 µg tilmanocept radiolabeled with 2.0 mCi (74 MBq) Tc 99m by injection as described in [Section 5.2](#).

7.2.6 Post Injection

Vital signs will be collected at 10 minutes, 30 minutes, and 1 hour post-injection. Vital signs will include respiratory rate, pulse rate, and systolic and diastolic blood pressures. Before blood pressures and pulse are obtained, the subject should be sitting quietly in a resting position for at least 1 minute. Body weight and height measurements are not required. Allowable windows for vital sign collection are as follow:

0:10, 0:30 = \pm 3 minutes

1:00 = \pm 5 minutes

7.2.7 Day 1: Imaging and Surgery

SPECT-CT will be performed prior to surgery as described in [Section 8.3](#) and in a manner consistent with the EANM clinical and technical guidelines for lymphoscintigraphy and sentinel node localization in gynaecological cancers as adopted by the SNMMI ([Giammarile et al., 2014](#)). All findings will be documented and recorded on the appropriate case report form (CRF). Dye (e.g., VBD or ICG) may be administered in the operating room immediately before surgical incision. The injection will be performed as deemed appropriate by the surgeon and in accordance with the standard of care at the clinical site. Imaging shall be completed prior to surgery and no greater than 20 hours after Lymphoseek injection, subjects will undergo ILM, SLN(s) will be harvested and surgery to remove the

primary tumor will be completed. Location of both hot and dye-identified nodes will be recorded on the sponsor-provided intraoperative worksheets.

7.2.8 24 ± 12 hours Postsurgical Safety Follow-up (telephone)

7.2.9 Adverse events and medications will be reviewed. End of Study

The 24 ± 12 hours Postsurgical Safety Follow-up call will serve as the end of study visit. FIGO staging will be reassessed post surgery by the PI and included with the final disposition.

8 PROCEDURES AND VARIABLES

8.1 Population Characteristics

8.1.1 Demographic and Other Baseline Characteristics

Forty female subjects 18 years of age or greater with known cervical cancer will be enrolled. Cancer characteristic including tumor size, cancer type and FIGO staging will be collected.

8.1.2 Medical and Surgical History

Medical and surgical history will be obtained on all trial subjects. All relevant medical conditions (current and prior), month/year of onset, and if the condition is currently active will be recorded in the CRFs. Common accepted medical terminology should be used.

8.1.3 ECOG Performance Status

All subjects will be evaluated at screening for Eastern Cooperative Oncology Group (ECOG) performance status (Table 2). The criteria below will be used to assign the ECOG grade.

Table 2. ECOG Performance Status

Grade	Description
0	Fully active, able to carry on all pre-disease performance without restriction
1	Restricted in physically strenuous activity but ambulatory and able to carry out work of a light or sedentary nature, e.g., light house work, office work
2	Ambulatory and capable of all self-care but unable to carry out any work activities. Up and about more than 50% of waking hours
3	Capable of only limited self-care, confined to bed or chair more than 50% of waking hours
4	Completely disabled. Cannot carry on any self-care. Totally confined to bed or chair
5	Dead

8.1.4 Prior and Concomitant Medication

All prior medication(s) used within the last 30 days before injection and concomitant medications will be documented. Medications administered for general surgical support and anesthesia related to surgery do not need to be captured in the CRFs.

8.2 Lymphoseek Preparation and Injection

Injection of Lymphoseek will be at study time 0:00. Subjects will receive an injection of 50 µg tilmanocept radiolabeled with 2.0 mCi (74 MBq) Tc 99m as described in [Section 5.2](#).

Local anesthetics are not permitted as co-injected drugs:, e.g., procaine, xylocaine, lidocaine or carbocaine.

8.3 Lymphoscintigraphy (SPECT/SPECT-CT Image Acquisition)

The SPECT camera used to obtain the images should be equipped with a low-energy, high-resolution collimator with a 20% window centered over a 140keV peak. The subject should be imaged in the same position used for surgery with arms positioned out of the field of view. Dynamic imaging should start at the time of injection and planar imaging should commence between 15 minutes and 20 hours post injection. Subjects should void their bladder just prior to imaging. It is strongly recommended that each site should perform all imaging acquisitions per their camera manufacturer and model parameters and in accordance with their institutional practices. All imaging should be completed prior to surgery no greater than 20 hours after injection.

For Sites using a SPECT camera:

Dynamic Imaging (optional)	Planar Imaging (mandatory)
Start at time of injection and continuously acquire until nodal uptake is seen, but for no longer than 1 hour.	To start after dynamic imaging (if performed) or to begin no sooner than 15 minutes post injection. Total acquisition time should not exceed 1 hour.

For sites using a SPECT/CT hybrid camera:

Dynamic Imaging (optional)	Planar Imaging (mandatory)
CT portion should be done prior to injection and start of SPECT. SPECT portion should start at time of injection and continuously acquire until nodal uptake is seen, but for no longer than 1 hour.	To start after dynamic imaging (if performed) or to begin no sooner than 15 minutes post injection. Total acquisition time should not exceed 1 hour. A CT scan for attenuation correction should be performed prior to each planar image.

Low-dose CT parameters for each institution's camera make/model should be utilized. SPECT data should be iteratively reconstructed and attenuation correction should be applied.

All images (non-corrected, corrected SPECT , CT and fused SPECT/CT) should be reviewed by a radiologist for quality.

[REDACTED] The number and anatomical location of each probable lymph node(s) identified preoperatively will be documented and captured in the eCRFs.

8.4 Surgical Procedures, Lymphatic Mapping, and Lymph Node Biopsy

8.4.1 Timing of Surgical Procedures

Between 1 to 20 hours after injection and imaging of Tc 99m Lymphoseek, subjects will proceed to surgery for intraoperative lymphatic mapping.

8.4.2 Lymphoseek-Designated “Hot” Nodes

Room Background Count

Using the handheld gamma detection system a room background shall be determined by recording three 2-second counts or one 10-second count obtained at least 30 cm away from the injected subject and any other radiation source.

Normal Tissue Background Count

Using the handheld gamma detection system, identify an anatomical region greater than 30 cm from the Lymphoseek injection site and not over the abdomen. A set of three 2-second counts or one 10-second count on non-lymphoid tissue (background counts) are obtained to set the threshold criteria.

In Vivo

Lymphoseek positivity is based on radioactivity counts derived from the application of the handheld gamma probe *in vivo*, where such counts must satisfy the threshold criterion of greater than the quantity of 3 times the square root of the mean normal tissue background count (i.e., standard deviation) added to the mean normal tissue background count (referred to as the “ 3σ rule”). Any nodal count NOT meeting this threshold criterion will be considered a negative finding (not localized). Use [Appendix 2](#) to assist in determining the 3σ level from the normal tissue background level.

Ex Vivo

Lymphoseek positivity is based on radioactivity counts derived from the application of the handheld gamma probe *ex vivo* (excised from the subject), where such counts must satisfy the threshold criterion of greater than the quantity of 3 times the square root of the mean normal tissue background count (i.e., standard deviation) added to the mean normal tissue background count (referred to as the “ 3σ rule”). Any nodal count NOT meeting this threshold criterion will be considered a negative finding (not localized). Use Appendix 2 to assist in determining the 3σ level from the normal room background level.

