8.4.3 Surgical Lymph Node Identification

1. If a dye (e.g., VBD or ICG) is to be used, it should be injected according to the standard practice of the clinical site.
2. On entering the subcutaneous tissue, a dye-containing lymphatic vessel or lymph node may be seen. If a dye-containing lymphatic vessel is seen, carefully trace it to the proximal LN. In vivo counts should be recorded and LN removed.

OR

If no dye-containing lymphatic vessel or lymph node is seen, then using a combination of visualization and the handheld gamma detector, explore the lymphatic basin for the LNs. As dissection proceeds towards the LN, repeated use of the handheld gamma detector is helpful in maintaining a line of site to the lymph node. The count rate will increase as dissection approaches the Lymphoseek-containing lymph node(s).

3. Once a LN has been identified, in vivo counts should be taken prior to excision. In vivo counts will consist of a set of three 2-second counts or one 10-second count (depending on the device) over the lymph node. Determination of a positive finding (i.e., localization) is based on the **In Vivo** definition above. Any LN count not meeting this threshold criterion will be considered a negative (non-localized) finding.
4. The method used to identify all LN(s) will be recorded (i.e., dyed appearance, Lymphoseek positive finding, or both) prior to excision.
5. To confirm the in vivo procedure, a set of three 2-second counts or one 10-second count will be recorded for the excised lymph nodes. The mean count of the ex vivo LN will be compared to the mean of normal tissue background counts, and the threshold criterion used to determine a positive finding for the in vivo LNs will be applied to the ex vivo specimens. The appearance and time of excision of the lymph node will be documented. Determination of a positive finding (i.e., localization) is based on the **Ex Vivo** definition above. Ex vivo counts must be performed on all excised lymph nodes

Table 3 describes the procedures that should be followed based on the in vivo and ex vivo status of the tissue that has been excised.

Table 3. Handling of Excised Tissue

In Vivo Assessment	Ex Vivo Assessment	Procedure
Radioactive Status		
positive (hot)	positive (hot)	Send to pathology for further evaluation.
positive (hot)	negative (not hot) or no counts obtained	Incorrect node harvested. Send to pathology for further evaluation. Return to resection bed.

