negative or no counts (not hot)	positive (hot)	Comment on why lymph node was removed. Send to pathology for further evaluation.
Dye Status		
dye-identified node	N/A	ANY dye-identified node is sent to pathology for further evaluation regardless of radioactive status.

6. A thorough evaluation of the remaining lymphatic basin should be undertaken since more than one LN may be found. This evaluation should include a combination of palpation, visualization, and gamma detector survey for evidence of dye and/or increased gamma detector count rates.
7. Probing of the area will be complete when all selected node counts are negative by use of the threshold criterion. The surgeon will continue with visualization and palpation according to local practice to ensure that no grossly positive LNs remain at the site of resection.

If a subject has neither a dye-identified node nor any “hot” nodes, continue with visualization and palpation according to your medical expertise.

Pelvic lymphadenectomy will be performed in accordance with institutional standards. Additional surgical intervention such as radical hysterectomy should be performed in accordance with the subject’s surgical plan and the discretion of the surgeon.

All removed LNs (SLNs and NSLNs) must be sent to pathology for using the minimum requirements of histopathological evaluation outlined in the trial pathology manual.

For the purposes of analysis, a sentinel lymph node is defined as being hot ex vivo (lymph nodes with counts above the 3σ rule threshold).

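### The ex vivo threshold that makes a node sentinel is defined on tissue background, but the worksheet instruction for it says room background

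*Combined protocol and SAP*

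**What the plan says.** Section 8.4.2 requires two background measurements. For the room: "Using the handheld gamma detection system a room background shall be determined by recording three 2-second counts or one 10-second count", taken away from the subject and other sources. No purpose is given for it there. For normal tissue, the counts "on non-lymphoid tissue (background counts) are obtained to set the threshold criteria".

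The Ex Vivo paragraph of 8.4.2 then sets the 3σ rule at "3 times the square root of the mean normal tissue background count (i.e., standard deviation) added to the mean normal tissue background count". The In Vivo paragraph uses the same formula. Each paragraph ends by pointing to Appendix 2. The In Vivo sentence names tissue background; the Ex Vivo sentence reads: "Use Appendix 2 to assist in determining the 3σ level from the normal room background level".

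Step 5 of section 8.4.3 says "The mean count of the ex vivo LN will be compared to the mean of normal tissue background counts" and that "the threshold criterion used to determine a positive finding for the in vivo LNs will be applied to the ex vivo specimens". It then refers the reader back to the Ex Vivo definition for the determination. Section 8.4.3 closes with the analysis rule: "For the purposes of analysis, a sentinel lymph node is defined as being hot ex vivo", by the 3σ threshold. Appendix 2 tabulates thresholds against an average count and does not say which background is to be looked up.

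**The concern.** Ex vivo status carries the primary endpoint. Under 9.4.1 and 9.9.3, a node-positive subject is a false negative if no sentinel node is positive, and a true positive if at least one is. Which nodes count as sentinel is decided by the ex vivo threshold. Sensitivity, negative predictive value (NPV), accuracy and the tumor detection rates use the same label.

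The room count must be recorded, and the Ex Vivo sentence is the only place that gives it a use. A site working from the look-up sheet could therefore enter the room value, while another site, or the programmer, enters the tissue value. Section 9.3 pools all centers, so mixed practice would not show in the results. Table 3 also ties a surgical action to ex vivo status. For a node hot in vivo but not hot ex vivo it reads "Incorrect node harvested. Send to pathology for further evaluation. Return to resection bed". The conflict is therefore not confined to the analysis.

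**Working it through.** **1. Which background each place names**

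| Place | Background |
|---|---|
| 8.4.2, Normal Tissue Background Count | tissue |
| 8.4.2, In Vivo: formula and Appendix 2 instruction | tissue, both |
| 8.4.2, Ex Vivo: formula | tissue |
| 8.4.2, Ex Vivo: Appendix 2 instruction | **room** |
| 8.4.3, step 5 | tissue, then refers back to the Ex Vivo definition |
| 8.4.3, analysis definition of sentinel node | 3σ rule, background not repeated |
| Appendix 2 | none named |

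One sentence disagrees with the rest. Step 5 does not fully settle it, because it refers back to the paragraph that contains that sentence.

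**2. Reproducing Appendix 2.** With background mean B, the threshold is T(B) = B + 3√B.
- B = 4: 4 + 3 × 2 = 10.00
- B = 25: 25 + 3 × 5 = 40.00
- B = 100: 100 + 3 × 10 = 130.00

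Twenty-one entries from 1 to 208 were checked and all match to rounding. The sheet is arithmetically right; its output depends entirely on which B is entered.

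**3. How far apart the two readings can be.** The documents give no counts, so these means are assumed.

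| Room mean | Tissue mean | T from room | T from tissue |
|---|---|---|---|
| 1 | 5 | 4.00 | 11.71 |
| 2 | 10 | 6.24 | 19.49 |
| 10 | 50 | 19.49 | 71.21 |
| 5 | 5 | 11.71 | 11.71 |
| 10 | 5 | 19.49 | 11.71 |

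Only a node whose ex vivo count falls between the two thresholds changes label. Nodes above both, or below both, are unaffected. Equal backgrounds change nothing.

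**4. Direction, with pathology results held fixed.** If room is below tissue, the room reading only adds sentinel nodes. A tumor-positive node that becomes sentinel makes its subject a true positive; a tumor-negative one changes no subject's class. False negatives can then only fall or stay the same. If room exceeds tissue, they can only rise or stay the same. The denominator, subjects with any positive node, does not depend on the label.

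**5. Effect on the FNR.** Inputs from 9.7: about 40 subjects, 20% node-positive, expected FNR 12.5%.
- Node-positive subjects: 0.20 × 40 = 8. False negatives: 0.125 × 8 = 1.
- Plan's own figure: the exact (Clopper-Pearson) 95% CI for 1/8 is 0.32 to 52.65%. Half the width is (52.65 − 0.32)/2 = 26.2, which agrees with the stated 26%.
- One subject is 1/8 = 12.5 points.

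Taking 1/8 as the result under the tissue threshold:

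| Change | FNR (95% CI) | NPV (95% CI) |
|---|---|---|
| None | 1/8 = 12.5% (0.3 to 52.7) | 32/33 = 97.0% (84.2 to 99.9) |
| One subject becomes true positive (needs room below tissue) | 0/8 = 0% (0 to 36.9) | 32/32 = 100% (89.1 to 100) |
| One subject becomes false negative (needs room above tissue) | 2/8 = 25.0% (3.2 to 65.1) | 32/34 = 94.1% (80.3 to 99.3) |

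The NPV numerator is 40 − 8 = 32 node-negative subjects. The denominator adds the false negatives.

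**The case against.** The best answer is that the analysis definition is clearer than the conflict suggests. It invokes the 3σ rule, which is written out twice, both times on tissue. The tissue paragraph says what its counts are for, and step 5 carries the in vivo criterion over to excised nodes. No section states a room-based criterion; the word appears once, in a sentence about a look-up aid. A programmer who traces the definition arrives at tissue, and a site using room would have to set aside the formula in the same paragraph. The study is also exploratory, tests no hypothesis, and already expects an interval of 0.3 to 52.7%. The counts needed to re-derive the label are taken under 8.4.2 and 8.4.3.

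Much of this stands. It makes a drafting slip plausible and keeps the importance down. It does not remove the conflict: the sentence is the operative instruction for the look-up sheet, and nothing says the analysis derives the label from counts rather than accepting the site's determination.

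Two stronger readings are tempting. A reader might infer that the FNR is materially biased. The documents do not support that, because they give no background or nodal counts, and a change needs a node between the thresholds that is tumor-positive in a subject with no other positive sentinel node. No probability can be put on that combination. A reader might also infer that the label changes the pathology work-up, since 8.5.1 sets a fuller minimum for sentinel than for non-sentinel nodes. That is possible but remains inference: 8.5.1 does not say which label the pathologist uses, 8.4.3 limits the ex vivo definition to analysis, and the trial pathology manual is not part of the documents.

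**Conclusion.** The ex vivo threshold is contradictory as written: the formula and step 5 say tissue, while the Appendix 2 instruction says room. It feeds the sentinel label behind the primary FNR, so the text needs reconciling. The weight of the text favors tissue as the intended meaning, but that does not guarantee uniform practice at 4 to 6 sites.

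The size of the effect is unknown. Each subject who changes class moves the FNR by 12.5 points. That figure rests on the protocol's expectation of 8 node-positive subjects and on pathology results staying fixed; it does not show that any subject will change. The move to 2/8 additionally requires room background to exceed tissue background. Importance is low to moderate: the contradiction is certain, the consequence is not, and the study is exploratory.

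**What to change.** 1. Reconcile 8.4.2 (Ex Vivo), 8.4.3 step 5 and Appendix 2 so that one named background sets ex vivo status at every site and in the analysis. Because Table 3 attaches a surgical action to that status, the choice of background is for the sponsor. Print the chosen background on the Appendix 2 sheet.
2. In 9.9.3, state that sentinel status is derived from the recorded ex vivo and background counts using that background. For subjects already enrolled, list every node whose label differs between the two backgrounds, and report how many subjects move between false negative and true positive.

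The cost is one protocol clarification, a sentence in section 9 and one listing. The documents do not say that raw counts reach the eCRF, so an added field or a source check may be needed. Relabelling afterwards cannot undo any pathology already done under the label in use at the time.
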